The identity and contact details of the participants will only be used for scheduling and carrying out the survey. The survey will assess the physician's level of awareness and understanding of the content of the educational material/SmPC. All information collected during the course of the survey will be kept strictly confidential.

Study Size

The medical records of at least 100-200 patients will be studied per country (sample would be representative dependent on country-specific volumes of edoxaban prescriptions) for 600 to 1,200 treated patients in total across the 7 targeted European countries.

For characterization of users including potential off-label use, we present the level of precision in different scenarios of available number of users of edoxaban for different prevalence of diseases and conditions. In general, the 95% level of confidence is adequate for a prevalence as low as 1% and 1,200 users of edoxaban.

The sample size has been estimated based on the distance from the assumed proportion of patients with off-label use to the limits of the corresponding 95% confidence Interval (CI). Table 2 presents the precision in the estimate of the proportion of the off label use of edoxaban out of the labelled indication for tentative proportions of 0.02, 0.03, 0.04, 0.05 (2%, 3%, 4%, 5%) and different sample sizes.

Table 2 - Precision of estimation for proportions of 0.02, 0.03. 0.04, 0.05 (2%3%, 4% 5%) of off label use and increasing sample size

Sample Size Scenario

	pr	oportion =	0.02	proportion = 0.03			proportion = 0.04			proportion = 0.05		
sample size	½ CI	L95%	U95%	½ CI	L95%	U95%	½ CI	L95%	U95%	½ CI	L95%	U95%
200	0.019	0.001	0.039	0.024	0.006	0.054	0.027	0.013	0.067	0.030	0.020	0.080
400	0.014	0.006	0.034	0.017	0.013	0.047	0.019	0.021	0.059	0.021	0.029	0.071
600	0.011	0.009	0.031	0.014	0.016	0.044	0.016	0.024	0.056	0.017	0.033	0.067
800	0.010	0.010	0.030	0.012	0.018	0.042	0.014	0.026	0.054	0.015	0.035	0.065
1000	0.009	0.011	0.029	0.011	0.019	0.041	0.012	0.028	0.052	0.014	0.036	0.064
1200	0.008	0.012	0.028	0.010	0.020	0.040	0.011	0.029	0.051	0.012	0.038	0.062

Note: CI: 2-sided 95% Confidence Interval (CI); ½ CI: distance from proportion to lower/upper limit of the two-sided 95% CI (equals half of the width of the CI); L95%:

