9.2. Setting

The study aims to include approximately 1,200 medical records of consecutive patients who were treated at least once with one or more dose(s) of edoxaban.

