9.2.1. Participating Sites

About 100 hospital- and office-based physicians (General Practitioners [GPs], internal medicine physicians and other specialists) in at least 7 Western European countries (Germany, Italy, Switzerland, the United Kingdom, Belgium, Spain and Portugal) are foreseen to participate in the study.

Country selection will take into account prescription volumes, the number of prescribers per capita, and favorable regulatory and ethical environment to conduct observational studies as well as the launch sequence of edoxaban in the different European countries. The sponsor may include additional European country(ies) based upon the actual use of edoxaban in initially-selected countries and to ensure selection reflects geographic representation among European countries.

Following the identification of the countries, an independent prescription data source (IMS LifelinkTM) will be used to identify a representative sample of the prescribers in each country. Based on these sources it is possible to retrieve general information on edoxaban number of prescribers per specialty and geographic region.

At least 100 prescribers of edoxaban will be recruited in 7 European countries following each country-specific product launch and the distribution of the health care professional (HCP) Educational Material. These could include GPs, cardiologists, internal medicine specialists (and other specialists) from a variety of settings (e.g., office-based vs. hospital-based, urban vs. rural).

Physicians participating in interventional programs for edoxaban will not be eligible to participate in the study. By applying this approach both representativeness and comprehensiveness of the sample in terms of types of prescribers are ensured.

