9.5. Study Size

The medical records of approximately 200 patients will be studied per country (sample would be representative dependent on country-specific volumes of edoxaban prescriptions) to approximately 1,200 treated patients in total across the 6 targeted European countries.

For characterization of users including potential off-label use, we present the level of precision in different scenarios of available number of users of edoxaban for different prevalence of diseases/conditions. In general, the 95% level of confidence is adequate for a prevalence as low as 1% and 1,200 users of edoxaban.

The sample size has been estimated based on the precision of a percentage, that is, the width of the 95% confidence Interval (CI). Table 2 (see summary page 17) presents the precision in the estimate of the proportion of use of edoxaban out of the labelled indication for tentative proportions of 0.02, 0.03, 0.04, 0.05 (2%, 3%, 4%, 5%) and different sample sizes.

Table 6 - Precision of estimation for proportions of 0.02, 0.03, 0.04, 0.05 (2%, 3%, 4%, 5%) of off-label use and increasing sample size

	Proportion											
	0.02			0.03		0.04		0.05				
Sample Size	½ CI	L95%	U95%	½ CI	L95%	U95%	½ CI	L95%	U95%	½ CI	L95%	U95%
200	0.019	0.001	0.039	0.024	0.006	0.054	0.027	0.013	0.067	0.030	0.020	0.080
400	0.014	0.006	0.034	0.017	0.013	0.047	0.019	0.021	0.059	0.021	0.029	0.071
600	0.011	0.009	0.031	0.014	0.016	0.044	0.016	0.024	0.056	0.017	0.033	0.067
800	0.010	0.010	0.030	0.012	0.018	0.042	0.014	0.026	0.054	0.015	0.035	0.065
1000	0.009	0.011	0.029	0.011	0.019	0.041	0.012	0.028	0.052	0.014	0.036	0.064
1200	0.008	0.012	0.028	0.010	0.020	0.040	0.011	0.029	0.051	0.012	0.038	0.062

Note: CI: 95% of Confidence Interval (CI); ½ CI: distance from proportion to lower/upper limit of the two-sided 95% CI (equals half of the width of the CI); L95%; L95%: lower limit of the 95% CI; U95%: upper limit of the 95% CI.

Table 2 shows that the width of the 95% CI decreases as sample size increases; samples greater than 500 patients enable the estimation of the proportion of off-label use with an acceptable degree of precision. Increasing the sample size beyond 600 patients shows additional (though small) effects on the width of the 95% CI. Therefore, the current aim of recruiting 1,200 patients will assure to receive reliable results.

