A sample size of 600 patients for instance will allow the detection of a rate of 5% of off-label with a precision of 1.7%, that is, the estimated proportion will be comprised between 3.3% and 6.7%. A sample size of 1,200 patients will allow for an even higher precision, as a rate of 5% of off-label is detected with a precision of 1.2%, that is, the estimated proportion will be comprised between 3.8% and 6.2%.

[figure not shown]

Figure 2 - Confidence Interval (CI) for half of CI width

In addition, it is estimated that approximately 100 physicians will have to complete the survey to allow reasonable precision around estimates of the physician's awareness and understanding levels.

In order to achieve robust results from the various statistical validation methods, it is recommended to have at least 10 physicians per questionnaire item/observation. This rule has been adopted as the standard for psychometric (fit for purpose) validation with its origin within the classical test theory of principal component analysis.⁴

No target thresholds for physicians reported awareness and understanding have been established in advance. However if it is assumed that 85% of physicians will demonstrate appropriate awareness and understanding of the survey. Given this, the lower bound of the 95% CI will be above 78% for a sample size of N=100.⁵

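### The planned precision for off-label use (±1.2 points at 5% and n = 1,200) assumes independent patients, although the charts are nested in about 100 prescribers

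*Protocol*

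**What the plan says.** Protocol section 9.5 bases the study size on the width of a two-sided 95% confidence interval for one percentage, the proportion of off-label use. Table 2 (section 4) and Table 6 (section 9.5) give the same grid of half-widths for proportions of 2% to 5% and sample sizes of 200 to 1,200. The text below Table 6 draws two figures from it:

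- "A sample size of 600 patients for instance will allow the detection of a rate of 5% of off-label with a precision of 1.7" points;
- at 1,200 patients, "a rate of 5% of off-label is detected with a precision of 1.2" points, so that "the estimated proportion will be comprised between 3.8% and 6.2" percent.

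The sampling is described elsewhere. Section 9.2: "The study aims to include approximately 1,200 medical records of consecutive patients". Section 9.2.1: "At least 100 prescribers of edoxaban will be recruited in 7 European countries"; the same section also gives the number as about 100. Section 9.2.2 asks for consecutive enrolment at each site as far as possible. Section 9.1 says that the chart data serve to assess how prescribers actually behave.

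Clustering, intraclass correlation and design effect appear in none of the study size (9.5), the data analysis (9.7) or the limitations (9.9). Section 9.7 provides for 95% confidence intervals but leaves the details to the SAP, which is not among the documents reviewed.

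**The concern.** Charts are sampled in two stages: prescribers first, then their patients. Patients of one prescriber share a decision-maker, a specialty, a local case mix and the same exposure to the educational material. Their on-label or off-label status is likely to be positively correlated, and each further chart from the same prescriber then adds less information than a chart from a new one. A formula for independent patients ignores this and gives too small a half-width.

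Off-label use is the quantity on which the study is sized, and section 9.5 concludes from these tables that 1,200 patients will give reliable results. If the tables overstate the precision, a regulator reading them expects tighter estimates than the design can deliver.

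A smaller point concerns the n = 200 row, which matches the planned number per country. There the normal approximation is used with only four expected cases at 2%, and it puts the upper limit too low.

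**Working it through.** **Inputs from the protocol.** Proportion p = 0.05 and n = 600 or 1,200 (9.5); two-sided 95% level (note to Table 2); about 1,200 charts (9.2); about, or at least, 100 prescribers (9.2.1).

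**Inputs assumed.** The protocol gives no ICC and no variation in charts per prescriber. I use ICC 0.01 to 0.20 and, first, equal numbers of charts.

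**Step 1: reproduce the plan's figures.** Half-width = 1.96 × √(p(1 − p)/n).

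- n = 1,200: 1.96 × √(0.05 × 0.95/1,200) = 0.01233, i.e. 1.2 points (3.77% to 6.23%).
- n = 600: 1.96 × √(0.05 × 0.95/600) = 0.01744, i.e. 1.7 points.

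All 24 half-widths in Tables 2 and 6 reproduce to three decimals in this way, so they contain no design effect.

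**Step 2: add the clustering.** DEFF = 1 + (m − 1) × ICC, effective n = n/DEFF, half-width = 1.96 × √(p(1 − p) × DEFF/n). With 100 prescribers, m = 1,200/100 = 12. Because 100 is also given as a minimum, the case of 200 prescribers (m = 6) is shown as well.

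| ICC (assumed) | DEFF, m = 12 | Effective n | Half-width, m = 12 | Half-width, m = 6 |
|---|---|---|---|---|
| 0.01 | 1.11 | 1,081 | ±1.30 | ±1.26 |
| 0.05 | 1.55 | 774 | ±1.54 | ±1.38 |
| 0.10 | 2.10 | 571 | ±1.79 | ±1.51 |
| 0.20 | 3.20 | 375 | ±2.21 | ±1.74 |

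Half-widths are in percentage points, at p = 5% and n = 1,200, against 1.23 for independent patients.

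For 600 charts from 100 prescribers (m = 6), the same ICCs give ±1.79, 1.95, 2.14 and 2.47 against 1.74.

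**Step 3: unequal numbers of charts.** DEFF = 1 + ((1 + CV²) × m − 1) × ICC. With m = 12 and an assumed coefficient of variation of 0.5, DEFF is 1.14, 1.70, 2.40 and 3.80, and the half-widths are ±1.32, 1.61, 1.91 and 2.40.

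**Step 4: compare with the plan's own marks (m = 12, equal numbers).** 1,200 charts are worth 600 independent ones when DEFF = 2, i.e. ICC = 1/11 ≈ 0.09. Effective n reaches the 500 that section 9.5 takes as its lower mark when DEFF = 2.4, i.e. ICC = 1.4/11 ≈ 0.127.

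**Step 5: coverage, if the analysis also assumed independence.** Coverage = 2Φ(1.96/√DEFF) − 1. With m = 12 this is about 94%, 88%, 82% and 73% at ICC 0.01, 0.05, 0.10 and 0.20.

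**Step 6: the n = 200, 2% cell.** The table formula gives 0.02 ± 1.96 × √(0.02 × 0.98/200) = 0.02 ± 0.0194, shown as 0.1% to 3.9%. The exact (Clopper-Pearson) interval for 4/200 is 0.55% to 5.04%. The upper limit in the table is 5.04 − 3.9 ≈ 1.1 points too low, before any clustering.

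**The case against.** The case against rests on five arguments.

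- **No ICC is given.** At 0.01 the loss is trivial (1.30 against 1.23 points). The sizing outcome is use outside the labelled indication, which also depends on the patient's diagnosis, so a high ICC should not be presumed. This stands: the direction is clear for any positive ICC, the size is not.
- **At least 100 prescribers is a minimum.** Twelve charts each is then roughly the largest average. This stands too, and the 200-prescriber column shows the gain. It reduces the loss without removing it.
- **The plan's own standard mostly survives.** With 12 equal charts per prescriber, effective n stays above 500 up to an ICC of about 0.127. The study is descriptive, and no off-label threshold depends on 1.2 points. A reader might infer that the study is too small; the documents do not support that.
- **The analysis method is left to the SAP.** A reader might infer that every planned interval is too narrow and that the reported ones will undercover. The protocol fixes no method for the reported intervals, so the coverage figures are conditional. The survey interval (85%, N = 100, lower bound 78%) has the physician as its unit, so chart clustering does not touch it.
- **Small country cells are already hedged.** Section 9.7 limits by-country analysis to what is reasonable, and the n = 200 row is only a planning illustration. Its 2% limits are still wrong as printed.

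A reader might also fault section 9.5 for calling the study adequate at a prevalence of 1%, since no table has a 1% row. That is not an error: the exact interval for 12/1,200 is 0.5% to 1.7% before clustering, which does not contradict the sentence.

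None of this makes the printed 1.2 points a property of the design, and a SAP does not correct a precision claim that stands in the protocol.

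**Conclusion.** The point holds for the planning precision of off-label use in section 9.5 and Tables 2 and 6. The arithmetic there is correct, but it answers for independent patients, which this design does not provide. At 5% and n = 1,200 the half-width is ±1.30 to ±2.21 points with 12 charts per prescriber, or ±1.26 to ±1.74 with 6, instead of ±1.2. These ranges rest on assumed ICCs of 0.01 to 0.20 and equal numbers of charts; unequal numbers make them wider. The shortfall is minor at the low end and material from an ICC of about 0.05. Separately, and without any ICC, the 2% cell of the n = 200 row understates the upper limit by about 1.1 points.

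This should be fixed, but it does not put the study in doubt: its conduct and size can stay as planned.

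**What to change.** 1. Restate Tables 2 and 6 and the sentences on 600 and 1,200 patients with a design effect, giving the assumed number of charts per prescriber and a stated range of ICCs with its justification.
2. Use Wilson or exact limits in the sparse n = 200 row; for 2% (4/200) the exact limits are 0.55% to 5.04%.
3. Add one sentence to section 9.7 that patient-level 95% confidence intervals allow for clustering by prescriber or site. The choice of method can stay in the SAP.
4. Leave the survey precision statement as it is.

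The cost is wording and a recalculated table. The stated precision becomes less favourable. No extra patients, sites or data are needed.

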9.6. Data Management (DM)

A data management plan (DMP) will be created that will describe all functions, processes, and specifications for data collection, cleaning and validation for the DUS.

High data quality standards will be maintained and processes and procedures utilised to repeatedly ensure that the data are as clean and accurate as possible when presented for analysis. Data quality will be enhanced through a series of programmed data quality checks that automatically detect out-of-range or anomalous data.

9.6.1. Data Entry/Electronic Data Capture

Mixed data capture will apply: The pseudonymized data will be entered into electronic Case Report Forms (eCRFs) by the site staff via a secure web-based electronic data capture (EDC) system. In sites that do not have the capabilities to access the internet to enter data, a provision will be made to collect pseudonymised data recorded on paper

CRFs. Sites will be instructed to maintain completed paper CRFs in a secure environment prior to dispatch to the CRO.

The EDC system will be a secure web-based system using specific encryption mechanisms for exchanging data between the web browser of the user and the data server. All users of the EDC system (Investigators and site personnel as well as sponsor/CRO staff) will be able to access their account with a unique personalized username and password. Users will be assigned certain standardized user roles that will allow/restrict them to perform specific actions within the EDC application. An audit trail will record any actions within the eCRF such as session times, user who accessed the data, initial entry or changes made to the data (including reason for change or correction).

In case of eCRF data capture the sites will directly enter the data from their patients' medical records into the standardized English eCRFs. Each participating site will have access to its enrolled patient data only. All sites will be fully trained on using the online data capture system, and on the eCRF completion guidelines and other help files. All eCRFs should be completed by designated, trained personnel as appropriate. The eCRF is to be reviewed, electronically signed, and dated by the investigator.

The eCRFs will include programmable edits to obtain immediate feedback if data are missing, out of range, illogical or potentially erroneous.

Edit checks within the eCRF may be checks tied to a certain field or edit checks across multiple fields.

Field checks may include the following:

- Checks on non-conformance (e.g., a non-existing date or a numeric field including text)
- Range checks on numeric fields (e.g., a field that has to be greater than x but lower than y)
- Checks on missing values (e.g., a predetermined required field)
- Checks on future dates

Edit checks across multiple fields may be any check firing on the condition of another field (or multiple fields) containing a certain value (or a range of values). These may be e.g. a relationship between a parent record and a sub-record or a comparison of different dates.

All edit checks will be listed in a Data Management document separate from the Observational Plan with a description of the check firing logic (including pseudo-code as necessary and any ranges defined, if applicable), the type of check and the query message text with reference to the applicable forms and items.

To ensure a high quality of data the Sponsor will take data snapshots at pre-defined time points and review the data for any potential data errors or discrepancies.

Ad hoc queries will be generated within the EDC system and followed up for resolution.

Paper CRFs completed by the sites will be collected by CRO staff and entered by trained CRO personnel into the EDC system. Queries will be posted on paper forms and sent to the sites for clarification.

The data from the project specific database will be exported into SAS data sets as per Clinical Data Interchange Standards Consortium (CDISC) Study Data Tabulation Model (SDTM) definition for further validation and analysis.

9.6.2. Source Documents

The source documents are contained in the patient's medical record and data collected on the eCRFs must be traceable to these source documents. All original source documentation is expected to be stored at the site for the longest possible time required by local applicable regulations. The site will be instructed to notify the Sponsor before any destruction of medical records of study participants.

The data will be reported as descriptive statistics for the variables already presented in section 9.3 (survey administration variables, description of survey population, and assessment of knowledge of the key messages of the educational program). Data will be presented overall, by country and by key characteristics (e.g. specialty of physician, geographic location, etc.).

Physicians who do not respond to the survey will be categorized into non-responders. Moreover, the responders and non-responders characteristics will be compared.

A comparison of responders and overall target population characteristics will also be performed.

9.8. Quality Control

This study will be conducted according to the rules of 'Good Pharmacoepidemiology Practice' (GPP) and the 'Guideline on Good Pharmacovigilance Practices (GVP) – Module VIII (Rev 1)' EMA/813938/2011 Rev 1. Related quality control mechanisms (e.g. data plausibility checks, monitoring of data) will be performed accordingly.

The physician will comply with the confidentiality policy as described in the site contract. The physician will comply with the observational plan and the requirements described in the contract. The physician is ultimately responsible for the conduct of all aspects of the study at the site and verifies by signature the integrity of all data transmitted to the sponsor.

During the site initiation visit, the monitor will provide training on the conduct of the study to the investigator, co-investigator(s), and all site staff involved in the study. In order to ensure the integrity of the data, sites will be monitored by a qualified monitor. A risk based monitoring approach will be conducted during the study to examine compliance with the protocol and adherence to the data collection procedures, to assess

the accuracy and completeness of submitted clinical data, and to verify that records and documents are being properly maintained for the duration of the study. This will include regular remote data monitoring and on site monitoring will be performed in 20% of the sites. During on-site monitoring, the monitor will verify 100% of informed consent documentation and perform source data verification against the patient's medical records in randomly selected patients (3 per site).

Data quality checks will be performed on an ongoing regular basis. Queries will be raised by the responsible CRO and shall be answered by the site in due course. The purpose is to ensure that the rights of the patients are protected, that the reported data are accurate and complete, and that the conduct of the study is in compliance with the observational plan and applicable regulatory requirements.

The monitor will close out each site after the last patient's final follow-up assessment is completed, all data have been entered and all outstanding monitoring issues have been resolved or addressed. All monitoring procedures will be described in a Clinical Operations Plan (COP). Monitor contact details for each participating site will be maintained in the Investigator Site File.

Representatives of the Sponsor's quality assurance unit/monitoring team and competent regulatory authorities must be permitted to inspect all study-related documents and other materials at the site, including the Investigator Site File, the completed eCRFs and the patients' original medical records. Audits may be conducted at any time during or after the study to ensure the validity and integrity of the study data.

